**CONFIDENTIAL** 

total of total of 5 years. Adverse events and pathology results will be recorded.

At the time of endoscopic follow up, biopsies of the treated area will be taken and submitted for analysis according to standard care for analysis at the JHH Pathology lab.

#### **Primary Endpoints**

- Device Performance
- Adverse events
- Efficacy for complete elimination (CE) of all esophageal dysplasia
- Efficacy for complete elimination of all BE

All adverse events

Esophageal stricture formation and assessment of clinical dysphagia.

#### Secondary Endpoints

Patient Pain

### 3.2 Study Purpose and Objectives

**Endpoints:** 

The purpose of this study is to assess the safety, feasibility, performance and the short- and long-term effectiveness of the C2 Focal Cryoablation Device in patients with BE and esophageal squamous dysplasia. Three times of ablation (5, 6, 8, 10 or 12 seconds) can be used and post-ablation symptoms related to the Cryoballoon Focal Ablation will be recorded. At 6 to 12 weeks, the patient will receive a follow-endoscopy to assess stricture formation along with biopsy samples taken.

The ultimate goal is to achieve 90% or greater ablation of BE and 100% ablation of all dysplastic areas.

Post-operative pain will be noted. Additionally, biopsy samples will be evaluated for the presence of residual Barrett's Esophagus. Through evaluation of the histological results, treatment parameters for the ablation of human esophageal epithelium will be better understood.

Evaluations include, but are not limited to the following:

- Deployment ease/scope compatibility.
- Device malfunctions.
- Time of catheter deployment.
- Adverse events.
- Stricture formation at 8 to 12 weeks.
- Patient Pain.
- Histological evaluation of treatment zone at 8 to 12 weeks for presence of residual Barrett's Esophagus.

#### 3.3 Study Population

The study population is patients who have BE or squamous dysplasia and meet the protocol entry criteria.

PROTOCOL# CP-0007/ Version: 8 29April 2019

**CONFIDENTIAL** 

<sup>3 Stricture formation is defined as none, mild (non-circumferential stenosis allowing easy passage of diagnostic endoscope), moderate (circular stenosis allowing passage of diagnostic endoscope), and severe (any stenosis preventing the passage of a diagnostic scope).

#### 3.4 Selection criteria

#### 3.5.1. Patient Selection Criteria

Inclusion Criteria (Candidates for this study must meet ALL of the following criteria):

- a) Patients scheduled for ablation, EMR, and/or surveillance for BE (with or without dysplasia) or esophageal squamous dysplasia. Patient is > 18 years of age at the time of consent (inclusive)
- b) Patient has provided written Informed Consent (IC) using an Informed Consent Form (ICF) that has been approved by the Institution's reviewing IRB/EC.
- Patient is willing and able to comply with all Clinical Investigation Plan (CIP) requirements.
- d) Patient is deemed operable per standard institutional criteria.

Exclusion Criteria (candidates will be excluded if ANY of the following conditions apply):

- a) Patient with endoscopically active inflammation in the treatment zone.
- b) Esophageal stenosis preventing advancement of a therapeutic endoscope
- c) Patient has a known history of unresolved drug or alcohol dependency that would limit ability to comprehend or follow instructions related to informed consent, post treatment instructions or follow-up guidelines.
- d) Patient refuses or is unable to provide written informed consent.
- e) Patients with uncorrectable coagulopathy, thrombocytopenia or on chronic anticoagulation unable to have "bridge" therapy for any standard endoscopy.
- f)

### 3.5.2. BE Selection Criteria

Inclusion criteria (BE areas in the treatment zone must meet ALL of the following criteria):

- Each patient has pathologically confirmed BE with a C&M classification of C≥0 and/or M≥1.
- b) BE lesion within the treatment zone should be flat.

Exclusion criteria (BE areas will be excluded if ANY of the following conditions apply):

Active esophagitis Grade B or greater.

a) Endoscopically visible abnormalities such as masses or nodules within 4 cm of the treatment zone. Neoplastic nodules or lesions must be treated first with EMR at least 4 weeks prior to planned treatment with the CbFAS.

#### 3.5.3 Esophageal Squamous Neoplasia Selection Criteria

Inclusion Criteria (squamous esophagus areas in the treatment zone must meet ALL of the following criteria):

- Each patient with esophageal squamous dysplasia must have dysplasia in the treatment area by prior Lugol's chromoendoscopy/narrow band imaging and targeted mucosal biopsies.
- b) The squamous lesion should be flat.

Exclusion Criteria (squamous esophagus areas will be excluded if ANY of the following conditions apply

PROTOCOL# CP-0007/ Version: 8 29April 2019

- a) Invasive squamous cell carcinoma
- b) Endoscopically visible abnormalities such as masses or nodules within 4 cm of the treatment zone. Neoplastic nodules or lesions must be treated first with EMR at least 4 weeks prior to planned treatment with the CbFAS

#### 3.5 Informed Consent, Screening, Enrollment, Treatment, and Follow-up

### 3.5.1 Stage 1) Patient Informed Consent

Written informed consent will be obtained prior to any study driven tests or procedures.

A member of the research team will approach the patient to obtain informed consent. The background of the proposed study, the procedure, the follow-up schedule and all potential benefits and risks will be carefully explained to the patient. The person obtaining consent shall:

- Avoid any coercion of or undue influence of subjects to participate.
- Not waive or appear to waive subject's legal rights.
- Use language that is non-technical and understandable to the subject or his / her legal representative.
- Provide ample time for the subject to consider participation.
- Include dated signatures of the subject or the subject's legal representative and of the clinical investigator.
- Ask whether the subject has any questions about the study.
- Copy signed ICF and provide to patient.

NOTE: The process of obtaining ICF will be documented.

The subject or his/her legal representative must sign the ICF approved by the study site's IRB/EC prior to enrollment. If the investigational procedure is to be filmed for educational purposes, this must also be carefully explained to the patient. An *example* ICF is included as **Attachment C**.

During the initial screening phase, the Investigator will perform an initial evaluation of potential study subjects for study eligibility. This initial screening phase may include review of existing patient information (review of medical history, medication, etc.).

For those patients that agree to participate in the study by signing the IRB/EC Approved ICF, a baseline evaluation will be performed (see **Table 2** for a schedule of assessments). If the baseline evaluation requirements listed in **Table 2** are available as part of the patient's routine examinations and medical history, they may not need to be repeated after the patient's IFC is obtained.

Subjects must undergo the investigational procedure within the timeframes indicated below:

- -Review of Medical History (within 7 days)
- -Review of medications taken (within 7 days)

Since final eligibility cannot be determined until the time of the procedure, it is expected that some study subjects may not undergo the cryoablation procedure (e.g. narrowing of the esophagus such that the endoscope cannot be advanced).

Subjects are considered enrolled at the time of introduction of the CryoBalloon Focal Ablation device.

#### 3.5.2 Stage 2) The Treatment

The treatment stage begins at the time of the ablation (endoscopy) procedure. Actual treatment time will vary by patient and will be documented. The treatment stage will be as follows:

PROTOCOL# CP-0007/ Version: 8 29April 2019

The subject is evaluated for the presence of strictures (if present, the stenosis should not
prevent advancement of a therapeutic endoscope or non-therapeutic endoscope with sidecar
external channel). Locate and record the gastroesophageal junction (top of gastric folds) by
depth of endoscope insertion.

### 2. For Barrett's esophagus patients:

- 3. Locate, measure, and record the depth of endoscope insertion at the most proximal circumferential extent of suspected columnar metaplasia. Locate, measure, and record the depth of endoscope insertion at the maximum extent of suspected columnar metaplasia. Document the number, and localization (insertion depth of the endoscope and orientation in the endoscopic field) of all BE islands. Document the level of the diaphragmatic pinch and size (length) of the hiatal/paraesophageal hernia.
- 4. Provide photo documentation of the entire Barrett's segment by taking one still image each centimeter of Barrett's epithelium. Endoscopic enhancements such as narrow band imaging should be performed to improve BE mapping and visualization.

#### 5. For esophageal squamous dysplasia patients:

- 6. Locate, measure, and record the depth of endoscope insertion at the most proximal metaplasia. Document the number, size (maximum and minimum diameter) and localization (insertion depth of the endoscope and orientation in the endoscopic field) of all squamous dysplasia lesions. Document the level of the diaphragmatic pinch and size (length) of the hiatal/paraesophageal hernia.
- 7. Provide digital videorecording and photo documentation of the entire esophagus(performed part of standard procedure documentation on EndoPro software, Pentax Medical Corporation) involved by neoplasia by taking one still image each centimeter from the GEJ to the proximal level of the abnormal esophageal areas. When possible, high definition videoendoscopes should be used for treatment and follow-up procedures. Endoscopic enhancements such as narrow band imaging and Lugol's chromoendoscopy (standard image enhancement techniques) should be performed to improve mapping and visualization prior to ablation. When Lugol's chromoendoscopy is performed, the endoscope channel must be flushed with 60 cc of water before passage of the cryoballoon to minimize staining of the balloon with dye.

#### For all Subjects:

- 8. The cryoablation will be performed to potentially treat all BE and squamous dysplasia, preferentially treating distal to proximal in a circumferential fashion. The goal would be to treat the entire BE area with 24 ablations or less during outpatient endoscopic treatment session.
- 9. All cryoablations will be preferentially performed with 10 seconds per site, but dosing can be adjusted to 5, 6, 8, 10 or 12 seconds according to the physician's judgement based upon degree of overlap with other ablations.

For BE patients: Additional "touch-up" 5 second ablations can be performed after endoscopic inspection of the treated areas show lack of typical post cryotherapy immediate tissue effects (erythema corresponding to vascular congestion/thrombosis).

For esophageal squamous dysplasia patients, the unstained esophageal mucosa after Lugol's chromoendoscopy ("Lugol's voiding lesions or LGLs", which correspond to dysplastic mucosa not taking up the dye) will be targeted.

10. The Cryoballoon Ablation Catheter is introduced inside either the accessory channel of the therapeutic endoscope, or the external working channel. The catheter is positioned and the

PROTOCOL# CP-0007/ Version: 8 29April 2019

**CONFIDENTIAL** 

ablation performed inside the identified area of BE. The use of CryoBalloon Focal Ablation System is in conformance to the IFU.

- 11. Document the location of the top and bottom of the ablation zone (insertion depth of the endoscope and orientation in the endoscopic field). This is done by videorecording, photo documentation and/or by recording the localization (of the ablated area). Placing a tattoo at the top of the ablation zone is optional to further identify the exact location of the ablation zone. Document the location of the tattoo (insertion depth of the endoscope and orientation in the endoscopic field).
- 12. Up to 5 outpatient ablation endoscopic procedures can be performed 8-12 weeks apart per patient (up to 24 per procedure) to achieve complete ablation of dysplasia. This treatment schedule is comparable to that for other standard endoscopic ablative techniques, such as radiofrequency ablation and carbon dioxide cryotherapy

#### 3.5.3 Stage 3) Patient Follow-up

The follow-up period begins immediately post-procedure. The patient will undergo a follow-up assessment immediately post-procedure / prior to discharge. The patient will undergo a safety phone contact at 1 days (±1 days), 8 (±1 days) days, and 1 month post treatment. Assessment of pain score (0-10 Likert scale), dysphagia score (0-4), odynophagia, diet, medications (including narcotic analgesics) will be performed using a standardized questionnaire.

### 3.5.4 Stage 4) Follow-up Endoscopy (8 to 12 weeks)

A high definition diagnostic scope can be used during the Follow-up Endoscopy stage unless warranted by institutional guidelines. If there is endoscopically apparent residual BE or squamous dysplasia at the follow-up procedure, this visit will become a treatment visit and cryoablation can be performed.

The Follow-up Endoscopy stage will be as follows:

- Locate and record the gastroesophageal junction (top of gastric folds) by depth of endoscope insertion. Locate, measure, and record the depth of endoscope insertion at the most proximal circumferential extent of suspected columnar metaplasia. Locate, measure, and record the depth of endoscope insertion at the maximum extent of suspected columnar metaplasia or squamous dysplasia. Document the number, localization (insertion depth of the endoscope and orientation in the endoscopic field) of all BE islands.
- 2. Document the location of the top and bottom of the ablation zone (insertion depth of the endoscope and orientation in the endoscopic field). This is done by videorecording or photo documentation and by recording the localization (of the ablated area).
- 3. Evaluate the presence of stenosis at the treatment zone.4
- 4. A biopsy (ies) will be performed according to standard of care, with targeted biopsies sampled from visible mucosal lesions and 4-quadrant random biopsies obtained from the 1 cm distal to the GEJ, the GEJ and every 1 cm proximal to the Z line, or the extent of the original BE or squamous dysplasia. The sample(s) will be collected and submitted as standard of care to Johns Hopkins pathology Thereafter, a representative photo of the biopsy site is taken.

PROTOCOL# CP-0007/ Version: 8 29April 2019

**CONFIDENTIAL** 

<sup>4 Stricture formation is defined as none, mild (non-circumferential stenosis allowing easy passage of diagnostic endoscope), moderate (circular stenosis allowing passage of diagnostic endoscope), and severe (any stenosis preventing the passage of a diagnostic scope).

 Treatment of residual BE and dysplasia with cryoballoon ablation using same technique, if indicated, will be performed, instead of endoscopic biopsy, if there is visible BE (for BE dysplasia patients) or unstained esophageal mucosa by Lugol's chromoendoscopy (for squamous dysplasia patients)

#### **SCHEDULES OF ASSESSMENTS**

An overview of the assessments to be performed along with the required timing is provided in **Table 2**. Visits occurring outside of the specified date range will be considered CIP deviations.

# 3.5.5 Stages 5 and 6 –12 24, 36, 48, 60 Month Assessments

1. As part of standard care, treated patients will be monitored by outpatient upper endoscopic procedures after completion of cryoballoon ablation (Stage 2), with EGDs every 3 months for first year (stage 5), then every 6 months for the second year to month 24 (stage 6). The endoscopic findings (detailed above) and pathology results will be documented at month 12,24, 36, 48 and 60 months for study endpoint analyses.

PROTOCOL# CP-0007/ Version: 8 29April 2019 CONFIDENTIAL 15 of 33

#### Table 2 - Schedule of Treatments and Assessments

\*Adverse events occurring prior to the procedure will be documented in the patient's medical record but will not count as related to the investigational device or procedure.

\*Treatments: Baseline or initial treatment visit = visit 0; subsequent treatments: 2nd to 5th treatment visits (10 weeks), as needed, up to 12 months from baseline. Treatments only if there is visible residual disease; no endoscopically- visible BE or abnormal squamous mucosa, biopsy will be performed using standardized protocol, beginning at the gastric cardia then the neo-Z line and every 1-2 cm proximal, to sample the previously treated BE areas (according to current standard of care).

Subjects can opt-out of participating in the surveillance phase of the trial after 12 months, if local endoscopic surveillance is preferred.

Adverse events: any patient with pain, dysphagia, fever, or other non-serious adverse event will be called weekly from day 8 to 1 month post-treatment or until AE resolution. Adverse events will be graded and recorded according to standard NIH definitions.

STUDY STAGES $\rightarrow$	Stage 1	Stage 2		Stage 3		Stage 4	Stage 5	Stage 6	
Assessments	Informed Consent/ Baseline Evaluation	Initial Treatment *	Immediately Post-/prior to discharge (up to 12 hours)	1-day Phone Contact (±1 day)	7-day Phone Contact (+/- 1 day)	30-day Phone Contact (+/- 1 day	EGD for treatment or biopsy ( q 8-12 weeks)	EGD for biopsy (endpoint assessment) (12 months)	EGD (24, 36, 48 and 60 months)
Consent	X								
Review of Medical History	x								
Review of Medications	Х	Х	X	Х	Х	Х	X		
Review of General Health	x	х	X	Х	X	X	x		
Physical Exam	X								
Pain and dysphagia Assessment		х	X	X	X	X	x	X	

PROTOCOL# CP-0007/ Version: 8 29April 2019

CONFIDENTIAL

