The international single arm CbFAS trial conducted under the original protocol for this study has been completed and the manuscript submitted to Endoscopy journal for publication. See more detail on the preliminary results in separate attachment submitted. In this multicenter, prospective non-randomized trial 39 patients were treated, each subject receiving 1-2 ablations of 6, 8 or 10 seconds. Symptoms were assessed directly and 2 days post-cryoablation. Follow-up endoscopy was performed after 6-8 weeks to assess the ablation response. Outcome parameters were incidence of adverse events, pain, esophageal stricture formation, and ablation response by cryogen dose. *Results*: 56 ablations (10 with 6-sec, 28 with 8-sec, 18 with 10-sec) were performed. Six ablations failed due to device malfunction (n=3) or other reasons (n=3). Median (IQR) procedure time was 7 min (4-10) min. No major adverse events occurred; six patients had a minor mucosal laceration requiring no intervention. Mild pain was reported in 27% of patients immediately after cryoablation and in 14% after 2 days. After 6-8 weeks no strictures had developed. Full squamous regeneration was seen in 6 [60%] of 6s-areas; 23 [82%] of 8s-areas, 100% of 10s-areas). These study results suggest that focal cryoablation of BE with the newly developed CbFAS is feasible, safe, and results in squamous regeneration in the majority of patients. These results were recently published (Scholvinck et al, Endoscopy July 2015 – paper uploaded into eIRB separately)

Furthermore, [name] has treated 41 BE patients and 10 patients with esophageal squamous low grade and high grade dysplasia (neoplasia) within this study and more treated within the clinical cryotherapy program at Johns Hopkins Hospital) with successful ablation in 1-3 outpatient procedures using multifocal cryoballoon ablations, in keeping with standard of care treatment approach to ablation. Research and clinical patients have tolerated cryoablation well, with visible treatment response.

Based upon the results of 2 clinical trials completed under this IRB-approved study,

[name] plans to continue this single center (industry sponsored) study to continue the evaluation of safety, effectiveness and 5-year durability of cryoballoon ablation for esophageal neoplasia.

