**Number of Sites:** 

**Study Procedures:** 

One institution: Johns Hopkins Hospital

The study will involve100 subjects with each subject receiving up to 24 ablations (multifocal) using the C2 System Focal Ablation System per treatment session. Ablations will be at 5, 6, 8, 10 or 12 seconds. Up to 5 treatment sessions 8-12 weeks apart within 12 months may be performed, if there is residual BE or abnormal squamous mucosa, until all disease is eliminated, by endoscopic biopsy. The ablations will be performed in an area of BE that is > 1cm 2 or recurrent BE at the gastroesophageal junction (GEJ).

Prior and intervening endoscopic mucosal resection (EMR) may be performed

for esophageal lesions, as part of standard care.

After completing cryoablation treatment, subjects return for EGD with

surveillance biopsy at every 2-3 months for first year and every 6 months for the second year as part of standard care then annually for next 3 years for

PROTOCOL# CP-0007/ Version: 8 29April 2019

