### 7.2 Binary Outcomes

Binary and ordinal outcomes will be tabulated. Confidence intervals for proportions will be calculated using the exact binomial distribution. A confidence interval approach will be used to compare outcomes with historical data.

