### 7.4 Missing Data

Missing values will generally be ignored in analyses. Imputation approaches, including last observation carry forward (LOCF) will not be used.

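### Five-year durability is an aim, but section 7 defines no recurrence event and no durability estimator, so months 24 to 60 give current status among attenders, from a time origin that is not fixed

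*Combined protocol and SAP*

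**What the plan says.** **The aim.** The section on preliminary experience says that the study continues for "evaluation of safety, effectiveness and 5-year durability of cryoballoon ablation for esophageal neoplasia". Section 3.2 includes the "short- and long-term effectiveness of the C2 Focal Cryoablation Device" in the study purpose.

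**The endpoints.** The efficacy items under Primary Endpoints in section 3.1 are CE of dysplasia and "Efficacy for complete elimination of all BE". No recurrence or durability endpoint is listed. Recurrent Barrett's esophagus (BE) is mentioned under Study Procedures in section 3.1, but only as an area that may be ablated, and it is not defined.

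**The analysis.** Section 7.0 describes a feasibility study with no hypothesis or comparison. For binary outcomes, section 7.2 provides tabulation and states: "Confidence intervals for proportions will be calculated using the exact binomial distribution". Section 7.4 states: "Missing values will generally be ignored in analyses". It also rules out imputation.

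**The visits.** Under section 3.5.5, endoscopic findings and "pathology results will be documented at month 12,24, 36, 48 and 60 months for study endpoint analyses". A note to Table 2 reads: "Subjects can opt-out of participating in the surveillance phase of the trial after 12 months, if local endoscopic surveillance is preferred". Section 3.7 requires every enrolled subject, including those withdrawn or lost, to be accounted for.

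**The time origin.** Study Procedures (section 3.1) and section 3.5.5 both place surveillance after ablation is complete. Table 2 sets visit 0 at the initial treatment, allows treatment up to 12 months from baseline, and states no origin for its 12-month and 24- to 60-month columns. Section 3.5.5 also attaches the label Stage 2 to completion, whereas Table 2 uses Stage 2 for the initial treatment.

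**The concern.** Durability concerns what happens after clearance: of the patients who reach CE, how many stay free of recurrence, and for how long. That needs an event, a set at risk, a time zero, and a rule for patients who leave. Section 7 supplies none of these.

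What it does supply, read with the opt-out note, is a proportion at each visit among those who attended. Two kinds of patient are then handled badly for a durability question. A patient whose recurrence is documented at month 24 and who then leaves is in no later proportion. A patient who recurs, is retreated under standard care and clears again may count as clear, because the plan does not say otherwise.

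At stake is the meaning of the 5-year figure, and of any comparison of it with historical data under section 7.2. The event, denominator and origin could also be settled after the data are seen.

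**Working it through.** The documents state no opt-out, recurrence or re-clearance rate, so there is no figure of the plan's own to reproduce. Every rate below is an assumption, used to show direction and range.

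**1. Attender proportion without retreatment.** Start with 100 patients, all in CE at month 12, with yearly visits to month 60 (four steps).

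- Recurrence *r* = 5% per year (8% in brackets).
- Opt-out *o* = 15% per year among clear patients.
- Opt-out after recurrence *d* = 5% to 50% per year.
- Each year, opt-out comes first, then new recurrence.

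Never recurred and attending: N(t) = N(t−1)(1−o)(1−r). Recurred and attending: R(t) = R(t−1)(1−d) + N(t−1)(1−o)r.

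True recurrence-free share at month 60: (1−r)⁴ = 0.95⁴ = 81.5% (0.92⁴ = 71.6%).

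At *r* = 5%, N runs 80.75, 65.21, 52.65, 42.52. The month-60 results, with differences taken before rounding, are:

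| *d* | R at month 60 | Attender proportion N/(N+R) | Difference from truth |
|---|---|---|---|
| 5% | 11.61 (17.83) | 78.5% (67.7%) | −2.9 (−3.9) |
| 15% | 9.68 (14.80) | 81.5% (71.6%) | 0 (0) |
| 25% | 8.04 (12.23) | 84.1% (75.4%) | +2.7 (+3.7) |
| 50% | 5.01 (7.51) | 89.5% (83.3%) | +8.0 (+11.6) |

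At *r* = 8%, N at month 60 is 37.40.

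Recurrences documented at months 24 to 60 total 12.7 (19.5) per 100. Subtracting those still attending gives 12.7 − 11.6 = 1.1 up to 12.7 − 5.0 = 7.7 patients (1.7 to 12.0) with a documented recurrence who are missing from the month-60 proportion.

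**2. With re-clearance.** Let 35% to 70% per year of earlier recurrences clear and count as clear, with the re-cleared leaving at 15% and no second recurrence. The attender proportion then exceeds the never-recurred share by +6.9 to +12.9 (+11.0 to +19.8) points. Setting *d* = 15% removes all selection, yet the gap is still about +8 at 35% and +12 at 70% (about +12 and +19). Most of the range is therefore a difference between two estimands, currently clear and never recurred. Only a small part is bias from leaving.

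The two effects can also cancel. At *d* = 5%, the difference is zero with re-clearance of 8.6% (7.5%) per year.

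**3. How the alternative behaves.** Kaplan-Meier, censoring at opt-out, targets (1−r)⁴ when opt-out among the never-recurred carries no information. Suppose instead that recurrence after opt-out is *k* times higher. Those who stay follow S(t) = S(t−1) × 0.85 × (1−r). Those who have left and not recurred follow O(t) = (O(t−1) + 0.15 S(t−1))(1−kr). The truth is S(4) + O(4):

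- *k* = 2: truth 76.2% (64.3%), so Kaplan-Meier is too high by 5.2 (7.3) points.
- *k* = 3: truth 71.6% (58.3%), so it is too high by 9.9 (13.3) points.

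**4. Time origin, from document figures only.** Sessions are 8–12 weeks apart, so *s* sessions end at (s−1) × 8 to (s−1) × 12 weeks:

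- one session: week 0;
- two sessions: weeks 8–12;
- three sessions: weeks 16–24;
- five sessions: weeks 32–48.

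This is the difference between counting from completion and counting from initial treatment. With five sessions, month 12 is week 52 on one count and weeks 84–100 on the other.

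**The case against.** **Feasibility.** With no hypothesis or comparison, a light analysis section is defensible, and durability appears among the aims rather than the endpoints. This stands as far as testing goes. A descriptive 5-year figure still needs an event, a denominator and a time zero.

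**CE at a visit is itself a current-status endpoint.** This stands. The visit proportions are legitimate and should remain; they answer a different question from durability.

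**Section 7.4 says only that missing values are generally ignored, and section 3.7 accounts for withdrawals.** That the result is status among attenders is an inference from sections 7.2 and 7.4 together. No alternative is named, however, and section 3.7 requires documentation, not an estimate.

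**Retreatment is thinly supported.** Study ablation is limited to 12 months, and no later ablation is described. Later retreatment under standard care is not excluded, but the re-clearance rates are pure assumption.

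**Kaplan-Meier is no cure.** This stands. Under the assumptions in step 3, its error is as large as the error it replaces.

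A reader might infer three stronger points, none of which the documents support:

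- *Opt-out makes durability look better than it is.* The stated reason for opting out is a preference for local surveillance, not disease status, and the difference can be negative, zero or positive.
- *The visit origin is wholly undefined.* Two sections tie surveillance to completion of ablation; what is missing is agreement with Table 2.
- *A shift of 32–48 weeks is typical.* It applies only to a patient who uses all five sessions, and the preliminary experience reports success in one to three.

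**Conclusion.** The concern holds as a gap between a stated aim and its analysis. Section 7 yields current status among attenders at months 24 to 60. It drops recurrences documented before opt-out from later figures, and it does not separate sustained clearance from re-clearance.

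Under the assumed rates without retreatment, the month-60 proportion differs from the recurrence-free share by −2.9 to +8.0 points at 5% recurrence per year and −3.9 to +11.6 at 8%. These figures show what is possible; the actual size and direction are unknown. The larger gaps with re-clearance should not be read as bias, since they arise mainly from a different estimand.

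The origin is not fixed, with 0–24 weeks at issue for one to three sessions and 32–48 for five. The change should be made because it is cheap and gives the durability aim a defined result. It is not needed to protect any test or sample size.

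**What to change.** In section 7:

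1. Keep the visit-specific CE proportions, labelled as current status among those assessed, with the denominator and the number not assessed.
2. Add time from first documented CE to first biopsy-confirmed recurrence, for BE and dysplasia separately, among patients who reach CE. Retain the event after any later clearance, and report how many never reach CE.
3. Estimate it by a censored time-to-event method (Kaplan-Meier or an interval-censored equivalent) with 95% confidence intervals, censoring opt-outs at their last endoscopy. Add one sensitivity analysis with higher recurrence after opt-out.
4. State one time origin per endpoint, and reconcile Study Procedures (section 3.1) and section 3.5.5 with Table 2.

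The cost is SAP wording and modest analysis work. Section 3.5.5 commits endpoint documentation only to months 12, 24, 36, 48 and 60, so case report form fields for interim endoscopy dates and findings may be needed. The durability figure may be less favourable, and it will rely on non-informative censoring, which the sensitivity analysis can probe but not remove. Requesting local endoscopy reports from patients who opt out would reduce that reliance; it is optional and would add consent wording and site work.
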